Until recently, Indonesia was among the few countries in which annual numbers of new HIV infections continued to rise (MoH, 2016). The latest epidemic modeling update indicated that except among men who have sex with man (MSM), annual numbers of new HIV infections had stabilized and begun to decline. However, with the current epidemic trajectory there would still be over 40,000 new HIV infections in the year 2030 (MoH,2016). Indonesia is not yet on course to end HIV and AIDS by 2030.

Although there has been a significant increase in the number of persons being treated for HIV/AIDS, the 108,479 people receiving ART as of December 2018 amounts to only 17 percent of the estimated number of PLHIV in the country (MoH, 2018). This makes Indonesia a performance “outlier” when compared to countries at comparable levels of gross national income (GNI) and health system development. The lack of more rapid progress has recently led key development partners to question Government of Indonesia (GOI) commitment to meaningfully addressing HIV and AIDS.

Insufficient HIV testing remains a barrier to increasing ART coverage. The number of HIV tests performed annually has risen steadily in recent years, reaching 3,077,653 in calendar year 2018 (MoH, 2018). However, pregnant women account for a sizeable proportion of the increased number of persons being tested. While commendable, the case detection “yield” from testing pregnant women is relatively low. More effective case finding strategies need to be implemented to reach population sub-groups with higher HIV incidence and prevalence, including key affected populations (KAPs) such as female sex workers (FSW). Unless Indonesia can significantly increase its volume and efficiency of HIV testing, it will not be able to reach the first “95” of the UNAIDS 95-95-95 framework – that is, 95% of PLHIV know their HIV status.

The main rationale is Indonesia’s concentrated epidemic transmission of HIV infection among KAPs, specifically FSWs. In 2016 it is estimated that there are 226,791 female sex workers throughout Indonesia (Table 1) and around 5,254,065 clients access their service per year (MoH, 2017). This mode of transmission continues to clients’ sexual partner and moreover, their babies. Lowering the transmission of HIV infection from FSW to their clients would simultaneously lower its transmission to their sexual partners and furthermore their babies.

In 2012, the estimated number of FSW and distribution FSW by “direct” (i.e., brothel-based) and “indirect” status is presented in Tabel-2. In 2016, the estimated number of FSW was not grouped into direct and indirect because it was considered that most of FSWs had shifted to becoming indirect due to Indonesia’s national policy to close brothels. Due to this policy, most FSWs have become hidden and hard to reach, thus increasing the challenge of increasing HIV testing uptake among this sub-population. Many commercial sex transactions have become underground, especially given the new popularity of digital platforms to sell sexual services. This phenomenon has created a new demand to identify alternative strategies for increasing HIV testing uptake among FSW.

Table 1. Estimated number of female sex workers (2016)

No	Province	Female Sex Workers		
		Point Estimate	Lower Estimate	Upper Estimate
1	Aceh	2,710	583	7,570
2	Sumatera Utara	14,234	8,079	21,943
3	Sumatera Barat	12,783	8,901	17,797
4	Riau	7,181	4,569	9,796
5	Jambi	4,544	1,986	7,188
6	Sumatera Selatan	7,630	4,235	11,323
7	Bengkulu	1,304	566	3,255
8	Lampung	7,532	4,534	10,717
9	Kep. Bangka Belitung	3,313	1,072	5,645
10	Kep. Riau	4,705	3,273	6,664
11	DKI Jakarta	21,405	17,444	25,386
12	Jawa Barat	25,281	17,806	34,220
13	Jawa Tengah	8,938	3,566	18,599
14	DI Yogyakarta	3,511	1,356	6,181
15	Jawa Timur	12,672	6,244	24,661
16	Banten	5,476	3,552	8,012
17	Bali	5,188	3,431	6,955
18	Nusa Tenggara Barat	2,127	1,131	3,212
19	Nusa Tenggara Timur	1,470	141	3,998
20	Kalimantan Barat	11,593	6,231	17,316
21	Kalimantan Tengah	5,208	1,580	11,181
22	Kalimantan Selatan	9,148	4,559	14,662
23	Kalimantan Timur	14,034	8,879	19,459
24	Kalimantan Utara	2,219	1,243	4,128
25	Sulawesi Utara	3,059	898	7,275
26	Sulawesi Tengah	6,052	1,663	10,801
27	Sulawesi Selatan	15,303	7,711	23,144
28	Sulawesi Tenggara	2,058	642	5,400
29	Gorontalo	746	111	2,722
30	Sulawesi Barat	1,376	250	3,076
31	Maluku	1,741	846	3,550
32	Maluku Utara	155	0	1,367
33	Papua Barat	542	326	1,780
34	Papua	1,553	706	5,330
	NATIONAL	226,791	128,114	364,313

Source: Ministry of Health (2016)

Table 2. Estimated number of direct (brothel) and indirect female sex workers (2012)

No	Province	Direct FSW	Indirect FSW
1	Aceh	2,179	929
2	Sumatera Utara	9,032	5,116
3	Sumatera Barat	3,089	2,197
4	Riau	3,643	2,758
5	Jambi	3,937	1,641
6	Sumatera Selatan	3,740	1,719
7	Bengkulu	1,235	1,403
8	Lampung	1,172	845
9	Kep. Bangka Belitung	481	472
10	Kep. Riau	1,195	1,312
11	DKI Jakarta	15,395	23,386
12	Jawa Barat	18,106	10,876
13	Jawa Tengah	13,205	10,023
14	DI Yogyakarta	1,945	706
15	Jawa Timur	14,381	10,459
16	Banten	2,798	1,365
17	Bali	3,378	3,464
18	Nusa Tenggara Barat	2,888	4,566
19	Nusa Tenggara Timur	7,245	6,427
20	Kalimantan Barat	1,695	2,150
21	Kalimantan Tengah	1,490	1,071
22	Kalimantan Selatan	845	1,476
23	Kalimantan Timur	1,041	759
24	Sulawesi Utara	1,315	1,360
25	Sulawesi Tengah	983	776
26	Sulawesi Selatan	1,646	1,627
27	Sulawesi Tenggara	913	1,096
28	Gorontalo	486	373
29	Sulawesi Barat	344	299
30	Maluku	1,233	1,082
31	Maluku Utara	535	635
32	Papua Barat	777	871
33	Papua	2,199	1,592
	NATIONAL	124,546	104,831

Source: Ministry of Health (2013)

2. HIV Testing Among FSW

Getting sufficient numbers of FSW tested for HIV has proven challenging globally (Tokar et al., 2018). While there is a sizeable literature on the efficacy of HIV prevention interventions for FSW (Kerrigan et al., 2015; Shahmanesh et al., 2008; Wariki et al., 2012; Wirtz et al., 2014), there is limited global evidence on the question of how best to increase rates of HIV testing among FSW. Although the WHO (2015) has recommended community testing approaches to supplement HIV testing at health facilities, the available evidence as to efficacy with FSW specifically is quite limited. A recent systematic review (Tokar et al., 2018) reported finding of 10 studies that examined recent testing in response to FSW HIV promotion interventions. Reported HIV testing uptake were varied, for example in Canada it was reported that 76% FSW had HIV test within the last one year (Deering et al., 2015), while in China only 22% FSW reported taking HIV test within the last one year (Park et al., 2011). Some reported barriers for FSW accessing HIV test service were financial, time, stigma, discrimination, low-risk perception, fear, lack of accessibility, reluctance from health service

providers to offer HIV testing and limited human resource. This literature review also showed that social support from peers and manager could increase HIV testing uptake in FSW (Tokar et al., 2018)

Community based HIV-testing has been implemented in some countries such as Vietnam (Nguyen et al., 2019), Uganda (Ortblad et al., 2018), Malawi and Zimbabwe (Napierala et al., 2019). Non-governmental organizations in Indonesia had conducted study or pilot project on HIV test in men who have sex with men (MSM) outside health facility (Hidayat et al., 2019). This study was done to find an alternative to facility-based HIV testing, however MoH has been rather conservative in supporting non-health facility-based approach outside of mobile clinic testing which involves trained healthcare professional to perform HIV testing procedure according to the algorithm developed by the government. Mobile clinic testing strategy gave out insufficient result, especially in terms of linking those with positive HIV result for further follow-up and initiation of treatment. Cost-effectiveness of this approach was also doubted, at least in Jakarta (Cantelmo et al., 2019). This study found that the cost needed for mobile testing to identify at least one HIV positive case among FSW was almost six-times fold higher compared to finding similar target among transgender and MSM, and seventeen-times fold higher than those for identifying one HIV positive case among people who inject drugs (PWID). For the effective use of resource, this study suggested modification of the test frequency, time, and location for FSWs in Jakarta. In addition, this study also recommended the need for alternative strategies to increase HIV test uptake among FSW.

FSWs community are at greater risk of not only HIV infection, but also stigma, discrimination and violence. They first face stigma and discrimination due to engaging in sex work itself, or from HIV stigma, particularly in contexts of HIV burden, which later affect their access to HIV testing (UNAIDS, 2016). The latest WHO guidelines have highlighted HIV self-testing (HIVST) as important tool to identify more people with undiagnosed HIV and at high risk of HIV infection. Protection of privacy and confidentiality is one of the advantages of this modality which allows for removing stigma as barriers to access services. HIVST has been shown to be acceptable across varieties of population globally including for FSWs community (King et al, 2013). Oral fluid HIVST is an alternative to traditional HIV testing services in the facility or other healthcare provider testing (UNAIDS, 2016).

3. HIV Self-testing Using Oral Fluid Test

One oral fluid test modality (OraQuick™) is currently waiting for the registration approval from Ministry of Health and expected to be available by March or April 2020. Evaluation of OraQuick™ in Thailand showed sensitivity of 90.14% (95%CI 80.74-95.94) and specificity of 99.13% (95%CI 97.78-99.76) (Rasmi et al., n.d.). A study assessing the acceptability of oral fluid rapid HIV 1 and 2 antibody test (OraQuick™) among key populations for HIV infection such as men who have sex with men (MSM), beach boys (BB), female sex workers (FSWs), and people who inject drugs (PWID) in Sri Lanka showed high level of acceptability for the test (Karawita et al., 2017). In China, most-at-risk populations showed high acceptability of oral fluid HIV rapid testing (OraQuick™), with suggestion for appropriate pricing and increased public health education through awareness campaigns that address concerns about its accuracy and safety (Xun et al., 2013). HIV-self testing kit distribution through key opinion leaders (KOLs) was feasible and oral self-testing was highly acceptable among urban MSM population in Nigeria (Tun et al., 2018). Linkage to treatment can be achieved with active follow-up and access to a trusted community clinic that offers HIV treatment and is MSM friendly (Tun et al., 2018).

4. Role of Outreach Worker in HIV Self-testing Using Assisted and Unassisted Method

In a study which assessed implementation and scale-up to HIV self-testing programs for female sex workers in Malawi and Zimbabwe, there were difference in preferences for how to access HIV self-testing, depended on how supportive the existing program infrastructure was (Napierala et al., 2019) In Zimbabwe, where there was a detailed understanding of the context of female sex workers and a ready framework to implement and evaluate HIV self-testing strategies, high acceptability (76%) and high accuracy of HIV self-testing was reported (Napierala et al., 2019). In contrast, peer-distribution models were favored by female sex workers in Malawi and female sex workers in Zimbabwe who were not engaged in the program (Napierala et al., 2019). Another study in Kampala (Uganda) evaluated HIV self-testing performance and results interpretation among FSWs who performed unassisted HIV self-testing, showed that misinterpretation of HIV self-test results were common among FSWs: 23% (12/56) of FSWs interpreted HIV-negative self-test results as HIV positive and 8% (3/37) of FSWs interpreted HIV-positive self-test results as HIV negative (Ortblad et al., 2018). The concordance between FSWs' instructions was 73% (95%CI 56% to 86%) for HIV-positive self-tests and 68% (95%CI 54% to 80%) for HIV-negative self-tests (Ortblad et al., 2018). This finding suggested training on use and interpretation of HIV self-test for the unassisted method might be necessary to prevent errors and to avoid the negative consequences of false-positive and false-negative HIV self-test results among FSWs.

5. Study Purpose

The study proposed in this protocol directly addresses the need to get more Indonesian FSW to “know their status” by providing an alternative, convenient HIV testing option in non-threatening community settings. In the Indonesian context where a reactive HIV test result using the MoH-mandated triple rapid test algorithm is needed to qualify for GoI-financed ART, community screening is seen as a mechanism for enabling FSW to conveniently determine their status and a facilitation mechanism for taking action based upon the community screening result, whether that entail going to a health facility for a confirmatory test in the case of a reactive screening result or adopting stronger prevention measures in the case of a non-reactive screening result, including PrEP as this prevention method is rolled out in Indonesia.

The study will produce scientifically strong evidence as to whether two alternative models of community HIV screening among FSW (assisted and unassisted) result in (1) increased rates of formal HIV testing at health facilities and (2) increased rates of treatment initiation in districts in which the community screening intervention is added to the existing FSW community outreach model.

Two alternative study protocols are described in this document. The bulk of this document presents a protocol for a community randomized controlled trial (cRCT), which is the preferred research design option. However, due to a delay in procurement of the OraQuick® rapid HIV test kits that are to be used in the study, there may be insufficient time to undertake a full cRCT.¹ Accordingly, a contingency protocol that can be implemented in a shorter period of time is also presented.

6. Study Objectives

The primary objectives of this study will provide answers to the following five (5) questions:

1. Does the proportion of FSW who know their HIV status increased?

¹ All research activities must be completed by 31 December 2020.

2. Does the introduction of community HIV screening among FSW increase the rate of HIV testing at health facilities?
3. Does “assisted” or “unassisted” community HIV screening among FSW result in a larger increase in the rate of HIV testing at health facilities?
4. Does “assisted” and “unassisted” community HIV screening among FSW results in a larger increase in the rate of HIV positive case finding?
5. Does the introduction of community HIV screening among FSW increase the rate of initiation of ART?

The secondary objectives of this study will provide answers to the following two (2) questions:

1. What is the acceptability of community-based self-screening for FSWs participating in this study?
2. What is the satisfaction of FSWs participating in this study towards delivery of community-based self-screening?

B. STUDY DESIGN

1. Design Summary

A Community Randomized Controlled Trial (cRCT) will be used for this study to explore in the HIVST evidence for FSWs in Indonesia with tests and treatment results in intervention acceleration districts compared to control districts with the current standard of care. In the trial, it is recommended the candidates will be tested using two approaches (assisted and unassisted), the latter via direct, fixed and other means of distribution system. A direct distribution system is where and FSW participant is directly given and HIVST by a peer, and a fixed distribution system is where the FSW participant collects the HIVST from a fixed point such as health clinic. Other distribution system may be implemented using courier services such as GO-JEK, etc. This trial aims to determine the acceptability, effectiveness and safety of these HIVST delivery approaches compared with standard of care for improving HIV testing coverage and knowledge of HIV status.

The study will be undertaken in the 23 “acceleration” districts in the National AIDs Program. These are: Kota Medan, Deli Serdang, Kota Palembang, Kota Bandar Lampung, Kota Tangerang Selatan, Tangerang, Kota Jakarta Selatan, Kota Jakarta Timur, Kota Jakarta Pusat, Kota Jakarta Barat, Kota Jakarta Utara, Bogor, Kota Bekasi, Kota Bandung, Kota Depok, Kota Semarang, Kota Surakarta, Kota Malang, Kota Surabaya, Kota Denpasar, Kota Makassar, Kota Sorong and Kota Jayapura. These are districts with high HIV prevalence among HIV key populations, including FSW, and have comprehensive ongoing HIV-TB intervention packages consisting of both health services and community prevention and support programs. As for the FSWs program, these 23 priority districts already implementing a comprehensive outreach package (reach to test and simplified case management for FSWs living with HIV). Table 3 below shows Global Fund targets for FSW HIV testing in 23 priority districts for 2019-2020. Table 4 shows achieved target of HIV testing per semester in 2018-2019 and estimated numbers of direct and indirect FSW in 2012 (MoH, 2013). Table 5 shows achieved target of outreach per year in 2018-2019 in 23 priority districts.

The flowchart of the study is presented in Figure 1. Randomization was carried out among the 23 priority districts in this study with a ratio of 2:1 (that is, 2 intervention districts per 1 control district). The details of randomization are explained in section B.4 of this document. **The assigned 15 intervention districts and 8 comparison districts** are described in Table 6. Potential participants in the intervention area will be screened through the inclusion and exclusion criteria established for

this study. The criteria for participants who are eligible for this study are explained in section B.3 of this document and Annex2.

According to the Indonesian Ministry of Health's current recommendation, HIV blood test at an authorized health facility is still the current practice for HIV diagnosis. Both participants in the intervention and comparison area will be offered for HIV blood test at a health facility. Participants in comparison areas and participants in intervention areas who agree to take HIV test at a health facility will then be managed further according to the existing guideline or "standard of care." For participants in intervention areas who refuses to have her blood drawn for HIV test at a health facility will then be offered self-testing using OraQuick®. Participants will then fill and sign the informed consent to participate in CBS study.

Next, participants will be offered to do the test assisted or unassisted. If the participant chooses to perform the test assisted, the PL/PE will help her from filling in a baseline survey, performing the test, and filling in a post-test survey. If the participant chooses to perform the test unassisted, there will be two options for the participant to get the test kit. First, PL/PE will deliver the test kit for the participant, help with filling in the baseline survey on the spot and give information about uploading test results and the post-test survey, along with a hotline number to call for any questions and concerns, including follow-up steps after participants have received the results. The second method, participants will be given a link online which will entitle information of this study, eligibility criteria, informed consent, baseline survey, link to order a test kit, link to upload result and link to fill in the post-test survey. Participant who chooses this second method will also be given hotline number should there be any further inquiries.

Participants with reactive or indeterminate result resulting from either assisted or unassisted methods will be encouraged to get a confirmatory test at a health facility. A confirmatory test will also be suggested for participants with non-reactive result. The difference between these two result groups will be the level of encouragement given to do the confirmatory test. While participant with reactive or indeterminate results will be strongly encouraged, participants with a non-reactive result will be suggested for a confirmatory test. These suggestions are derived from Indonesia's current guideline on HIV detection, where the confirmatory test is to be done at the health facility using the HIV blood test.

Figure 1. Study Flowchart

[figure not shown]

Table 3. Global Fund HIV testing targets in 23 districts for 2019-2020

No	Province	Districts	Region	Target of HIV Testing			
				P3	P4	P5	P6
1	Sumatera Utara	Kota Medan	1	904	904	1,002	1,002
2	Sumatera Utara	Kab. Deli Serdang	1	406	406	450	450
3	Sumatera Selatan	Kota Palembang	1	1,371	1,371	1,520	1,520
4	Lampung	Kota Bandar Lampung	1	393	393	435	435
5	Banten	Kota Tangerang Selatan	1	223	223	247	247
6	Banten	Kab. Tangerang	1	820	820	909	909
7	DKI Jakarta	Kota Jakarta Selatan	1	536	536	594	594
8	DKI Jakarta	Kota Jakarta Timur	1	877	877	973	973
9	DKI Jakarta	Kota Jakarta Pusat	1	1,341	1,341	1,486	1,486
10	DKI Jakarta	Kota Jakarta Barat	1	1,318	1,318	1,461	1,461
11	DKI Jakarta	Kota Jakarta Utara	1	1,431	1,431	1,586	1,586
12	Jawa Barat	Kota Bogor	2	474	474	525	525
13	Jawa Barat	Kota Bekasi	2	248	248	275	275
14	Jawa Barat	Kota Bandung	2	582	582	645	645
15	Jawa Barat	Kota Depok	2	374	374	415	415
16	Jawa Tengah	Kota Semarang	2	510	510	565	565
17	Jawa Tengah	Kota Surakarta	2	172	172	190	190
18	Jawa Timur	Kota Malang	3	84	84	93	93
19	Jawa Timur	Kota Surabaya	3	1,173	1,173	1,300	1,300
20	Bali	Kota Denpasar	3	1,407	1,407	1,559	1,559
21	Sulawesi Selatan	Kota Makassar	3	1,444	1,444	1,600	1,601
22	Papua Barat	Kota Sorong	4	438	438	485	485
23	Papua	Kota Jayapura	4	786	786	871	871

Table 4. Achieved target of HIV testing per semester in 23 priority districts (2018-2019)

No	Kab/Kota	Region	Achieved target of HIV testing per semester
1	Kota Denpasar	3	982
2	Kota Makassar	3	866
3	Kota Palembang	1	694
4	Kota Jakarta Utara	1	612
5	Kota Medan	1	575
6	Kota Surabaya	3	568
7	Kota Jakarta Barat	1	544
8	Kota Bandung	2	487
9	Kota Jakarta Timur	1	479
10	Kota Jakarta Pusat	1	473
11	Kota Jakarta Selatan	1	448
12	Kota Sorong	4	415
13	Kab. Tangerang	1	391
14	Kota Bogor	2	374
15	Kota Jayapura	4	323
16	Kota Bandar Lampung	1	319
17	Kota Depok	2	287
18	Kota Malang	3	243
19	Kota Tangerang Selatan	1	184
20	Kota Bekasi	2	158
21	Kota Surakarta	2	144
22	Kota Semarang	2	129
23	Kab. Deli Serdang	1	80

Table 5. Achieved target of outreach per year in 23 priority districts (2018-2019)

No.	Kab/Kota	Region	Achieved target of outreach per year
1	Kota Denpasar	3	5100
2	Kota Jakarta Barat	1	4947
3	Kota Jakarta Pusat	1	4004
4	Kota Palembang	1	3741
5	Kota Surabaya	3	3510
6	Kota Jakarta Timur	1	3157
7	Kota Jakarta Utara	1	3129
8	Kota Jakarta Selatan	1	2905
9	Kota Medan	1	2858
10	Kota Makassar	3	2683
11	Kota Bandung	2	2164
12	Kota Bogor	2	1961
13	Kota Bandar Lampung	1	1933
14	Kabupaten Tangerang	1	1374
15	Kota Semarang	2	1317
16	Kota Sorong	4	1220
17	Kota Surakarta	2	1190
18	Kota Depok	2	1107
19	Kota Tangerang Selatan	1	994
20	Kota Jayapura	4	983
21	Kabupaten Deli Serdang	1	939
22	Kota Bekasi	2	879
23	Kota Malang	3	877

2. Study Period

The study timeline is presented below. The study will be conducted from February 2020 to November 2020 (10 months). The preparatory activities will be conducted in February to March 2020. **The intervention will be implemented from April – October 2020 (7 months)**, with the last one months of 2020 allocated for data analysis, report writing and a workshop presenting study findings.

Study timeline

Activities	Month									
	Feb	March	April	May	June	July	Aug	Sept	Oct	Nov
1. Study preparation										

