18	Kota Malang	3	243	Intervention
19	Kota Tangerang Selatan	1	184	Intervention
20	Kota Bekasi	2	158	Comparison
21	Kota Surakarta	2	144	Intervention
22	Kota Semarang	2	129	Comparison
23	Kab. Deli Serdang	1	80	Intervention

Table 7. Allocated intervention districts

No	Kab/Kota	Region	Achieved target of HIV testing per semester (2018-2019)	Group
1	Kab. Deli Serdang	1	80	Intervention
2	Kota Medan	1	575	Intervention
3	Kota Palembang	1	694	Intervention
4	Kab. Tangerang	1	391	Intervention
5	Kota Tangerang Selatan	1	184	Intervention
6	Kota Jakarta Barat	1	544	Intervention
7	Kota Jakarta Pusat	1	473	Intervention
8	Kota Jakarta Timur	1	479	Intervention
9	Kota Bogor	2	374	Intervention
10	Kota Depok	2	287	Intervention
11	Kota Surakarta	2	144	Intervention
12	Kota Surabaya	3	568	Intervention
13	Kota Malang	3	243	Intervention
14	Kota Denpasar	3	982	Intervention
15	Kota Sorong	4	415	Intervention

Table 8. Allocated comparison districts

No	Kab/Kota	Region	Achieved target of HIV testing per semester (2018-2019)	Group
1	Kota Bandar Lampung	1	319	Comparison
2	Kota Jakarta Utara	1	612	Comparison
3	Kota Jakarta Selatan	1	448	Comparison
4	Kota Bekasi	2	158	Comparison
5	Kota Semarang	2	129	Comparison
6	Kota Bandung	2	487	Comparison
7	Kota Makassar	3	866	Comparison
8	Kota Jayapura	4	323	Comparison

5. Recruitment and Sample Size

All FSW in intervention districts who meet study eligibility criteria will be offered community screening (see Section C below for intervention implementation guidelines). FSW in comparison districts will continue to receive the current standard package of interventions.

In to be able to detect a 10 percentage point difference in the rate of HIV testing at health facilities between FSW in intervention vs. comparison districts and have 95% certainty that a difference of that magnitude would not have occurred by chance and 90% certainty of detecting a difference of this magnitude if the difference was real/”the truth,” the following sample of FSW will be needed in intervention and in comparison districts:³

$$n \geq [Z_{1-\alpha} (2P(1-P))^{1/2} + Z_{1-\beta} (P_1(1-P_1) + P_2(1-P_2)^2 / (P_1-P_2)^2)] * deft$$

Where:

$Z_{1-\alpha}$ = the Z score for the level of statistical confidence, or statistical precision, desired (for 95%, $Z = 1.96$)

$Z_{1-\beta}$ = the Z score for the desired statistical power (for 90% one-sided test, $Z = 1.282$)

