P_1 = the expected population proportion in the comparison group of districts (set = 0.5 – this is the worst-case scenario and will produced a sample size that is adequate irrespective of the actual proportion)

P_2 = the expected population proportion in the intervention group of districts (set = 0.6 – assume minimum effect size to be realized of 10 percentages points)

$$P = (P_1 - P_2) / 2$$

$(P_1 - P_2)$ = the magnitude of comparison-group differences (or change over time) to be detected with the specified level of precision and power (assumed to be +/- 10 percentage points)

deft = design effect to compensate for clustering at the district level (1.5 assumed).

The required sample size is thus $n \geq 635$ per experimental group; ≥ 761 after 20% allowance for lost-to-follow up

³ Source: Lwanga SK and Lemeshow S. Sample Size Determination in Health Studies: A Practical Manual. Geneva: World Health Organization.

Interpretation: we would need to recruit 761 FSW who self-test for HIV testing in the intervention districts and 761 FSW for HIV testing at health facilities in comparison districts to be able to detect a 10 percentage point difference in the rate of HIV testing at health facilities (intervention vs. comparison districts) to have 95% certainty that a difference of that magnitude would not have occurred by chance and 90% certainty of detecting a difference of this magnitude if such a difference existed.

In order to assess whether “assisted” or “unassisted” community HIV screening among FSW results in a larger increase in the rate of HIV testing at health facilities, we would need samples of size $n \geq 761$ each of FSW who received assisted and unassisted screening in intervention districts, a total of $n \geq 1,522$ FSW in intervention districts, plus $n \geq 761$ in comparison districts.

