In the event that participants' data are collected by paper, a procedure to upload the data into the established online system will be developed. Each data manager in the IUs needs to conduct the procedure regularly. This is to ensure that all data are being captured thoroughly.

F. DATA ANALYSES

The data analyses to be undertaken will be directed to addressing the research questions laid out at the beginning of the protocol and statistical tests appropriate to each specific analysis will be performed to inform the interpretation of results. The specific steps in the data analysis will be as follows:

1. Compare the characteristics of FSWs who receive self-testing and blood testing.

2. Compare the characteristics of FSWs who receive assisted and unassisted self-testing.
3. Compare proportion of FSWs taking confirmatory test out of those who receive the test in the assisted and unassisted self-testing.
4. Compare the proportion of FSWs who receive HIV test out of those who got offered for the test (including self-testing) in the intervention group with proportion of FSWs who receive HIV test in the control group.
5. Compare the proportion of FSWs taking confirmatory test (including self-testing) out of those receive the test in intervention groups and control group.
6. Compare the proportion of HIV positive in the assisted, unassisted (intervention) and HIV positive in the control group.
7. Compare the proportion of ART initiation in the assisted, unassisted (intervention) and the control group.
8. Calculate the cascade of HIV testing and treatment.
9. Compare stigma scores and FSWs who went to a health facility for HIV testing between assisted, unassisted group.
10. Compare the HIV and STI risk behaviors between assisted and unassisted group.

G. CONTINGENCY STUDY DESIGN

Should the OraQuick® test kits not become available in sufficient time to conduct a full-scale cRCT, a smaller-scale study will instead be undertaken. The purpose of the smaller study is the same as the cRCT described above, and the same protocol described above will be implemented. But the comparison is achieved targets between before and after intervention – there will be no comparison districts. The study will be undertaken in three (3) districts. The three districts will be selected from different parts of Indonesia, and they are: Kota Bandung (west part of Indonesia), Kota Denpasar (central part of Indonesia), and Kota Makassar (center-east part of Indonesia).

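### Five questions are all primary with no deciding contrast or error rule, and no analysis step tests facility testing between arms, the contrast the sample size rests on

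*Combined protocol and SAP*

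**What the plan says.** Section A.6 opens its list with "The primary objectives of this study will provide answers to the following five (5) questions". The five are: knowledge of HIV status; facility testing; assisted versus unassisted screening on facility testing; positive case finding; and ART initiation. They are not ranked.

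The aim is described differently elsewhere. A.5 asks whether the screening models "result in (1) increased rates of formal HIV testing at health facilities and (2) increased rates of treatment initiation". B.1 compares delivery approaches with standard of care "for improving HIV testing coverage and knowledge of HIV status".

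B.5 sizes the study on facility testing, intervention versus comparison districts, with "95% certainty that a difference of that magnitude would not have occurred by chance" and 90% power. It then reuses the same number for assisted versus unassisted. For treatment initiation it concedes too little power in the study sample and turns to SIHA data.

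Section F lists ten steps and says that "statistical tests appropriate to each specific analysis will be performed to inform the interpretation of results". Item 4 compares receipt of any HIV test, self-tests included. Item 5 compares confirmatory testing, again with self-testing included. Item 6 reads "Compare the proportion of HIV positive in the assisted, unassisted (intervention) and HIV positive in the control group", and item 7 does the same for ART initiation. No significance level, order, alpha split or exploratory label is given.

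**The concern.** There are two linked gaps.

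First, with five co-equal primary questions and no success rule, a significant result on any one of them could be reported as the primary finding. The single error statement in B.5 covers one comparison at a time and does not describe that family. Significance is not incidental here: A.5 promises strong scientific evidence, and Section G treats statistical significance as what would show that the intervention worked.

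Second, the contrast that justifies the sample size has no matching analysis. The nearest step, item 4, counts a kind of test that exists in one arm only. The routine-recording table in E.3 collects self-screening data in intervention districts and none in comparison districts. Item 4 can therefore rise because kits were handed out, whatever happens to attendance at facilities. Followed as written, the plan could leave Objective 2 untested between arms and let another primary question carry the claim.

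**Working it through.** **1. The plan's own figure.** Inputs from B.5: P1 = 0.50, P2 = 0.60, 90% power (z = 1.282), multiplier 1.5. I take P as the average, 0.55.

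n = [z_α √(2P(1−P)) + z_β √(P1(1−P1) + P2(1−P2))]² / (P1−P2)² × multiplier

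- z_α = 1.96, multiplier 1.5 (inputs as listed): 518.2 × 1.5 = 777.3, so 778 (779 if the base n is first rounded up to 519).
- z_α = 1.645 (one-sided 5%), multiplier 1.5: base n rounds up to 423; 423 × 1.5 = 634.5, so 635.
- z_α = 1.96, multiplier √1.5 = 1.2247: 518.2 × 1.2247 = 634.7, so 635.

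The stated 635 is reached by either of the last two routes but not by the inputs as listed. B.5 attaches "for 90% one-sided test" to the power term only, so the sidedness of the intended test is unclear. At n = 635 with multiplier 1.5, two-sided 5% power is about 83%.

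**2. Matching objectives to analysis steps.**

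| Objective (A.6) | Sized in B.5? | Section F step |
|---|---|---|
| 1. Knows status | No | Nearest is item 4 (any test, self-tests included) |
| 2. Facility testing, intervention vs comparison | Yes | None for facility testing alone; items 4 and 5 include self-tests |
| 3. Assisted vs unassisted, facility testing | Same n reused | Item 3 (confirmatory tests) |
| 4. Positive case finding | No | Item 6 |
| 5. ART initiation | Power conceded as insufficient; SIHA data proposed | Item 7 |

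Item 9 mentions facility attendance, but only between assisted and unassisted participants.

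**3. How far item 4 and Objective 2 can part.** Assumed inputs: 50% accept facility testing in both arms; 40% of intervention refusers self-screen; 10% of those later test at a facility. n = 635 per arm, design effect 1.5.

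- Any test: 0.50 + 0.50 × 0.40 = 0.70 versus 0.50.
- Facility test: 0.50 + 0.50 × 0.40 × 0.10 = 0.52 versus 0.50.

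z = difference / √(1.5 × 2p(1−p)/n), with p the mean of the two proportions.

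- Any test: p = 0.60; SE = √(1.5 × 2 × 0.24/635) = 0.0337; z = 0.20/0.0337 = 5.9.
- Facility test: p = 0.51; SE = √(1.5 × 2 × 0.2499/635) = 0.0344; z = 0.02/0.0344 = 0.6.

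Range for the assumed linkage: at 20% facility testing is 54% (z about 1.2), and at 30% it is 56% (z about 1.7). Reaching the 10 points in B.5 needs 0.10/0.20 = 50% of self-screeners to attend. The any-test result is the same throughout.

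**4. Family-wise error, five questions each at two-sided 5%.** The 5% is an assumption for the family, because Section F sets no level.

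- Independent: 1 − 0.95⁵ = 0.226.
- Common correlation (assumed), simulated with 2 million draws: 0.183 at 0.5 and 0.102 at 0.9.
- Only favourable results counted for Objectives 1, 2 and 5, which ask about an increase, and either direction for 3 and 4: 1 − 0.975³ × 0.95² = 0.164 if independent; by simulation 0.137 at 0.5 and 0.086 at 0.9.
- Bounds for five two-sided tests: 5% (perfect correlation) to 25% (Bonferroni).

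**The case against.** The best defence is that an ordering is implicit. B.5 sizes facility testing between arms first, then assisted versus unassisted, and then sets treatment initiation aside for SIHA data. That stands as evidence of what the authors had in mind. It is not a decision rule, and Section F does not carry it through.

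It can also be said that five distinct questions need no joint error control. Even so, the choice among primary outcomes that may disagree stays open until the data are seen, and Objective 2 still lacks an analysis step.

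Several stronger readings are not supported:

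- A reader might quote a single inflated error rate such as 18%. That needs an assumed correlation of 0.5, and the documents give none. It also counts a significant fall in testing as a success.
- A reader might expand items 6 and 7 into pairwise tests and count about nine primary comparisons. The items do not say pairwise, a global three-group test fits their wording, and Objective 5 is a single contrast.
- A reader might infer that facility testing will fall in intervention districts. The blood test is offered first and self-testing only after refusal (B.1, C.1), so a fall has to be assumed. With equal acceptance the outcome is flat to somewhat higher.
- A low linkage rate is likewise an assumption. C.5 pays participants 100,000 IDR towards a confirmatory test after either screening result, which could raise it.

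**Conclusion.** The concern holds in this form: five unranked primary questions, no rule for which decides, and no between-arm test of the outcome behind the sample size. These follow from the text alone.

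The sizes are conditional. The chance of at least one false significant result is about 23% for five independent two-sided 5% tests, falling to 18% and 10% at correlations of 0.5 and 0.9. It is about 16%, 14% and 9% when only favourable results count for Objectives 1, 2 and 5. All of these exceed 5%, but none is a figure the documents fix. The contrast between any testing (z about 5.9) and facility testing (z about 0.6) is an illustration from assumed acceptance, uptake and linkage; it shows that divergence is possible, not that it is expected. Correcting the plan before analysis needs wording and one added step, and no larger sample on this account.

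**What to change.** In A.6 and Section F:

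1. Name Objective 2 as the single primary contrast.
2. Add a Section F step comparing the proportion of offered FSW who are tested at a health facility, all intervention versus all comparison districts as randomised. Exclude self-tests, and include later confirmatory facility tests after any screening result. State whether the 5% level is one-sided or two-sided, and reconcile this with n = 635.
3. Report item 4 (any test, self-tests included) separately, as a secondary outcome for Objective 1.
4. Label Objectives 3, 4 and 5 secondary or exploratory, reported as estimates with 95% confidence intervals.
5. Fix the role of Objective 1 before analysis. Testing it in sequence after Objective 2, or sharing alpha with it as a co-primary, are both defensible. A.5 gives knowledge of status real weight, so this is the sponsor's choice.

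Cost: Objectives 3 to 5 lose stand-alone confirmatory claims. Rows 1 to 4 of the E.3 table already record facility testing in both groups. The gap is facility testing after non-reactive assisted screens: row 9 covers reactive screens only, and the list covering either result applies to unassisted screening. Those tests must be counted, using the confirmatory-test data that C.5 already pays facilities to collect. If alpha is shared, power for Objective 2 falls and the sample size should be rechecked.
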